## 1 Overview

SMART is a multicenter, single-arm prospective registry. Its primary objective is to acquire postmarket data on the use of the Penumbra SMART COIL® System (Smart) in the treatment of intracranial aneurysms and other malformations.

Approximately 1,000 subjects with intracranial aneurysms or other malformations treated by Smart will be enrolled across up to 100 sites. All subjects will be allocated to treatment with at least 75% Smart, Penumbra Coil 400™ (PC 400), or Penumbra Occlusion Device (POD®) coils as defined by the number of coils implanted.

The primary efficacy endpoint is the rate of retreatment through one year  $\pm$  6 months follow-up. The primary safety endpoint is the rate of procedural (within 24 hours of arterial puncture) device-related serious adverse events.

The secondary efficacy endpoints for the registry are the ability to achieve adequate occlusion at immediate post-procedure (Class I or II Raymond-Roy Occlusion Classification for aneurysms) and the number of times re-access with guidewire was required due to catheter kickout while using SMART/POD/PC 400.

This Statistical Analysis Plan (SAP) elaborates on statistical methods outlined in the registry protocol and presents analysis conventions. The SAP will be signed off before database lock.

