## 2 Sample Size

The predetermined sample size of approximately  $n = 1000$  subjects allows the primary efficacy and safety endpoints to be estimated with greater than  $\pm 2\%$  precision: re-treatment at one-year follow-up (95% CI: 6.6% to 10.0%) and procedural device-related serious adverse events (95% CI: 0.93% to 2.5%).

This analysis applies 95% two-sided binomial proportion confidence intervals using normal approximations to the binomial (SAS v 9.4; SAS Institute, Cary, NC).

These estimates assume 8.3% retreatment through one-year follow-up based on the mean rate observed in eight prior studies cited in the protocol, as weighted by their subject sample sizes. A 1.7% rate of procedural device-related serious adverse events is assumed based on data on file at the sponsor.

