## 4 Analysis Populations

### 4.1 Definitions

The ITT population will consist of all subjects who sign the informed consent and are enrolled in the registry with Smart, PC 400, or POD accounting for 75% or more of the total number of coils implanted. The ITT population will include only the first lesion treated for each subject. Summary statistics will be developed separately for additional lesions.

The PP population will be constructed by excluding subjects who have major protocol violations that impact endpoint evaluations. Subjects will be classified as screen failures if they are not consented or are consented and not enrolled due to failure to implant at least 75% Smart, PC 400, or POD coils or other reasons.

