## 9 Subgroup Analysis

The following subgroup analyses will be performed for the primary and secondary effectiveness and safety endpoints:

- Actual adjunctive treatment used: Balloon, Stent, Other, None
- Age: < 65,  $\geq 65$
- Aneurysm location: Extradural ICA, ICA, ACA, MCA, Posterior Circulation, Venous Circulation, Other
- Aneurysm size: Small (Up to 10 mm in the largest diameter), Large (> 10 mm to 25 mm in the largest diameter), Giant (> 25 mm in the largest diameter)
- Aneurysm status: Ruptured, Unruptured
- Lesion nature: Aneurysm, Arteriovenous malformation, Fistula, Other
- Lesion treatment technique: Constructive, Deconstructive
- Neck width: Small neck (< 4 mm neck width), Wide neck ( $\geq 4$  mm Neck Width or Dome-to-Neck ratio (defined as Dome Width / Neck Width)  $< 2$ )
- Vessel treatment at admission: Initial treatment, Retreatment

For re-access with guidewire due to catheter kickout, which is analyzed based on 0, 1, 2, and  $\geq 3$  kickout events, subgroup analyses will be performed using the Wilcoxon rank-sum test for subgroup variables with two levels and the Kruskal-Wallis test for subgroup variables with more than two levels. For the other three categorical endpoints, subgroup analysis will be performed using Fisher's Exact test.

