### Pooling Across Centers

| Pooling Across Centers | Adjunctive Treatment Used (Yes/No) | Age ≥ 65   | Aneurysm Location: ICA | Aneurysm Size: Small | Aneurysm Status: Ruptured | Lesion Nature: Aneurysm | Lesion Treatment Technique: Deconstructive | Neck Width: Wide neck | Vessel Treatment at Admission: Retreatment |
|------------------------|------------------------------------|------------|------------------------|----------------------|---------------------------|-------------------------|--|-----------------------|--|
| 99999                  | X.X% (n/N)                         | X.X% (n/N) | X.X% (n/N)             | X.X% (n/N)           | X.X% (n/N)                | X.X% (n/N)              | X.X% (n/N)                                 | X.X% (n/N)            | X.X% (n/N)                                 |
| 99999                  | X.X% (n/N)                         | X.X% (n/N) | X.X% (n/N)             | X.X% (n/N)           | X.X% (n/N)                | X.X% (n/N)              | X.X% (n/N)                                 | X.X% (n/N)            | X.X% (n/N)                                 |
| ...                    |                                    |            |                        |                      |                           |                         |  |                       |  |
| P-value                | X.XXX                              | X.XXX      | X.XXX                  | XXXX                 | X.XXX                     | X.XXX                   | X.XXX                                      | X.XXX                 | X.XXX                                      |

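### The two neck-width subgroups overlap: an aneurysm with a neck under 4 mm and a dome-to-neck ratio under 2 is both small-necked and wide-necked, and the SAP does not say which group it joins

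*SAP*

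**What the plan says.** SAP Section 9 lists nine subgroup variables to be examined for the primary and secondary effectiveness and safety endpoints. The neck-width entry begins "Neck width: Small neck (< 4 mm neck width), Wide neck". The wide-neck rule then has two limbs joined by an or: a neck of at least 4 "mm Neck Width or Dome-to-Neck ratio (defined as Dome Width / Neck Width") below 2.

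The same section names the tests. For catheter kickout, "subgroup analyses will be performed using the Wilcoxon rank-sum test for subgroup variables with two levels". For retreatment, adequate occlusion and procedural device-related serious adverse events, "For the other three categorical endpoints, subgroup analysis will be performed using Fisher's Exact test".

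Two other places bear on the point:

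- SAP Section 4.1: "The ITT population will include only the first lesion treated for each subject". Each subject therefore contributes one aneurysm, and any overlap comes from the definitions, not from multiple lesions.
- SAP Appendix, Pooling Across Centers shell: neck width appears there as a single column, "Neck Width: Wide neck", reported by site.

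The protocol does not define neck width. Neither document says what to do with an aneurysm that meets both definitions.

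**The concern.** Small neck is defined by width alone. Wide neck can be reached by width or by ratio. Any neck under 4 mm that is more than half the dome width satisfies both.

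Fisher's exact test and the rank-sum test compare independent groups, so each subject must sit in exactly one. Section 14 of the SAP says the subgroup table is repeated for every subgroup. The shell has a rate, a 95% confidence interval and a p-value for each level, so a small-neck column and a wide-neck column must both be filled. Without a rule, either some subjects are counted twice or the allocation is settled during programming, possibly after the data can be seen. Different choices give different group sizes, rates and p-values from the same data. The neighbouring age and aneurysm-size entries have clean cut-points and do not raise this problem.

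**Working it through.** The plan states no figure on this point, so there is none to reproduce. The first step is set logic; the others are illustrations on stated assumptions.

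**1. Do the definitions partition the aneurysms?** Write N for neck width and D for dome width, in mm.

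- Small: N < 4.
- Wide: N ≥ 4, or D/N < 2.
- Both: N < 4 and D < 2N.
- Neither: N ≥ 4 and N < 4 at once, which is impossible.

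Example: N = 3, D = 5 gives D/N = 1.67, so small and wide. N = 3.5, D = 6 gives 1.71, again both. On a grid of N from 1 to 8 and D from 1 to 25 in 0.5 mm steps there are 15 × 49 = 735 cells. The cells in both groups number 2 + 4 + 6 + 8 + 10 + 12 = 42, for N = 1, 1.5, 2, 2.5, 3 and 3.5. None is in neither group. The definitions are exhaustive but not exclusive. (The 42 cells demonstrate overlap; they do not estimate how common it is.)

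**2. What does double counting do to the test?** From the documents: about 1,000 subjects (SAP Section 1) and 8.3% retreatment (SAP Section 2). Assumed: all 1,000 are evaluable aneurysms, 350 with N ≥ 4 and 650 with N < 4, and 25% of the 650 (162) have D/N < 2.

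- Literal groups: small 650, wide 350 + 162 = 512, total 1,162 entries for 1,000 subjects.
- Exclusive groups: small 650 − 162 = 488, wide 512, total 1,000.
- If 10% to 60% of the 650 overlap (65 to 390 subjects), the literal total runs from 1,065 to 1,390.

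Suppose every subject has the same true rate p. With o shared subjects, the variance of the difference in rates is p(1 − p) × [1/n_S + 1/n_W − 2o/(n_S n_W)]. A test that assumes independence omits the last term.

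- 25% overlap: 1/650 + 1/512 = 0.003492; 2 × 162/(650 × 512) = 0.000974. The true variance is 0.72 of the assumed one, a standard-deviation ratio of 0.849. The nominal 1.96 cut-off acts as 1.96/0.849 = 2.31, a two-sided size of about 2.1%.
- 50% overlap (325 subjects, wide 675): 1/650 + 1/675 = 0.003020; 2 × 325/(650 × 675) = 0.001481. Ratio 0.51, standard-deviation ratio 0.714, cut-off 2.75, size about 0.6%.

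Simulating Fisher's exact test 4,000 times at 8.3% agrees: 1.9% and 0.4% with double counting, against 4.4% and 3.9% with exclusive groups. Double counting makes the test conservative.

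**3. Does the allocation change the table?** Invented event counts, 25% overlap case: 42 events in the 350 with N ≥ 4, 19 in the 162 overlap subjects, 29 in the remaining 488.

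| Handling of overlap | Small | Wide | Difference (points) | Fisher p |
|---|---|---|---|---|
| Wide takes precedence | 29/488 = 5.9% | 61/512 = 11.9% | 6.0 | 0.001 |
| Small takes precedence | 48/650 = 7.4% | 42/350 = 12.0% | 4.6 | 0.020 |
| Counted in both | 48/650 = 7.4% | 61/512 = 11.9% | 4.5 | 0.011 |

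**4. How large is the overlap?** The documents cannot answer this. With lognormal neck (median 3.0 to 3.5 mm, log SD 0.35) and dome (log SD 0.40), correlation 0.3 to 0.5, the overlap as a share of necks under 4 mm is:

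- dome median 5 to 7 mm: about 29% to 76%;
- dome median 8 to 10 mm: about 6% to 27%.

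Every parameter here is assumed. The width of the range is the finding: the share is not known.

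**The case against.** The best reply is that the SAP plainly intends a partition. It calls for the rank-sum test on variables with two levels, and a two-level variable gives each subject one value. Counting subjects twice is the least natural reading. The ratio limb of the wide-neck rule would do nothing unless it moved some necks under 4 mm into the wide group, and the pooling shell treats wide neck as a yes/no attribute. All this points to wide taking precedence, with a short exclusion missing from the small-neck definition.

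Most of that stands as a reading of intent. It does not supply the rule. The small-neck definition is just as explicit as the wide-neck one, and a programmer who applies it as written gets 650 in the illustration, not 488.

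Three stronger readings are tempting, and the documents do not support them:

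- *That the pooling table is also affected.* It uses only the wide-neck group, which is completely defined. Nothing there depends on small neck.
- *That the subgroup tests would produce spurious findings.* In the illustration double counting lowers the rejection rate under no difference; the risk is a missed or diluted contrast.
- *That a known, large fraction of subjects is affected.* No neck or dome distribution appears in either document, so any percentage reflects its assumptions.

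**Conclusion.** The point holds as a defect of definition. In SAP Section 9 an aneurysm with a neck under 4 mm and a dome-to-neck ratio under 2 meets both neck-width definitions, and nothing in either document decides between them. This follows from the text alone and needs no assumption. As written, the groups do not meet the independence requirement of the planned tests; any other handling is an unstated choice.

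The consequence is limited. It touches one of nine subgroup variables in a single-arm registry whose results are mainly descriptive. No overall primary or secondary estimate, confidence interval or sample-size statement relies on it. The conservative test sizes (about 2% and below 1%) and the three-way table rest on the assumed 350/650 split, the assumed overlap shares and, for the table, invented event counts. They show direction and mechanism, not the registry's expected result. It is worth correcting because the correction is cheap and makes the table reproducible.

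**What to change.** In SAP Section 9:

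- keep wide neck as neck width ≥ 4 mm OR dome-to-neck ratio < 2;
- change small neck to neck width < 4 mm AND dome-to-neck ratio ≥ 2.

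Every aneurysm with both measurements then falls in exactly one group; on the grid above, all 735 cells do. The pooling shell stays as it is.

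The cost is one line of wording. Both measurements are already part of the SAP's own definition, so no new data item is needed. Section 1 has the SAP signed off before database lock and Section 13 provides for documented changes, so the edit can be made and recorded through the existing route, preferably before any neck-width results are tabulated.

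### Age and aneurysm size are tested for retreatment only after grouping; a labelled supplementary analysis on the measured values would recover power if risk changes smoothly

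*SAP*

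**What the plan says.** SAP section 9 plans subgroup analyses of the primary and secondary effectiveness and safety endpoints.

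- **Age** enters with two levels, cut at 65.
- **Aneurysm size** enters with three ordered classes. It begins "Aneurysm size: Small (Up to 10 mm in the largest diameter" and goes on to large (up to 25 mm) and giant (above 25 mm).
- **Neck width** enters with two classes. The wide class is met by a neck of at least 4 mm or by a dome-to-neck ratio below 2.

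Kickout counts are compared with the "Wilcoxon rank-sum test for subgroup variables with two levels and the Kruskal-Wallis test for subgroup variables with more than two levels". For retreatment, adequate occlusion and the safety endpoint: "For the other three categorical endpoints, subgroup analysis will be performed using Fisher's Exact test".

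The subgroup shell in the SAP appendix prints each level's rate and 95% interval with a p-value column, and section 14 gives p-values to three decimals. Logistic and Cox models appear only in section 11, for differences between sites. Age is available as a number: the Demographics table summarises it by mean, SD and range, and the listing gives it per subject.

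**The concern.** Age and largest diameter are graded quantities. Cutting age at 65 treats a patient of 40 like one of 64. Cutting diameter at 10 mm treats a 3 mm aneurysm like a 9 mm one. A gradient within a group then contributes nothing to the test. For size, Fisher's exact test on three classes also makes no use of the fact that giant exceeds large and large exceeds small.

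Few events are expected: at the planning rate, 1,000 × 0.083 = 83 retreatments. Because the plan commits to printing p-values, a reader of the results may take a large one for age or size as showing no relation to retreatment, when the test had only a moderate chance of detecting one.

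**Working it through.** **Inputs from the documents.** About 1,000 subjects and an 8.3% retreatment rate (SAP section 2: "These estimates assume 8.3% retreatment through one-year follow-up"); cuts at 65 years and at 10 and 25 mm, and Fisher's exact test (SAP section 9).

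**Assumed, because the documents do not give them.** Two-sided 0.05 for subgroup tests; age with mean 57 and SD 13 (27% aged 65 or over); diameter log-normal with median 6 or 7 mm and log-SD 0.5; log-odds of retreatment linear in age or in log diameter, with odds ratio (OR) 1.25 to 1.5 per SD; every subject counted as having an aneurysm in the diameter runs.

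**The plan's own figure.** SAP section 2 uses "95% two-sided binomial proportion confidence intervals using normal approximations to the binomial". The half-width is 1.96 × √(0.083 × 0.917 / 1000) = 1.96 × 0.00872 = 0.0171. The interval is 6.59% to 10.01%, which matches the printed 6.6% to 10.0%. The documents state no power for any subgroup test, so there is no further figure to reproduce.

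**Simulation.** 1,500 datasets per setting. Fisher's test on the SAP groups (Freeman-Halton for three classes), the Cochran-Armitage trend test on the same three classes, and a one-term logistic likelihood-ratio test on the measured value:

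| Variable | n | OR per SD | Fisher on groups | Trend on classes | Measured value |
|---|---|---|---|---|---|
| Age | 1,000 | 1.25 | 31% | – | 48% |
| Age | 1,000 | 1.4 | 60% | – | 82% |
| Age | 1,000 | 1.5 | 75% | – | 94% |
| Age | 800 | 1.4 | 51% | – | 73% |
| Diameter, median 6 mm | 1,000 | 1.25 | 27% | 31% | 49% |
| Diameter, median 6 mm | 1,000 | 1.4 | 50% | 56% | 82% |
| Diameter, median 6 mm | 1,000 | 1.5 | 69% | 75% | 94% |
| Diameter, median 7 mm | 1,000 | 1.25 | 31% | 36% | 50% |
| Diameter, median 7 mm | 1,000 | 1.4 | 58% | 62% | 85% |
| Diameter, median 7 mm | 1,000 | 1.5 | 75% | 80% | 93% |
| Diameter, median 7 mm | 800 | 1.4 | 52% | 56% | 75% |

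At n = 1,000 the loss is 17 to 22 points for age and 18 to 32 for diameter. The step from Fisher to trend, which is the part due to ignoring order, is about 3 to 6 points. The rest of the diameter loss comes from grouping. With OR 1.0, every method rejected in 4.0% to 5.5% of datasets, so the comparison is fair on type I error.

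**Analytic check for age.** A two-way split at share q keeps φ(z)² / [q(1 − q)] of the information. With q = 0.27, z = 0.613 and φ(z) = 0.3306, this is 0.1093 / 0.1971 = 0.555. Power of 82% on measured age implies a noncentrality of (1.96 + 0.90)² ≈ 8.2. Multiplied by 0.555 this gives 4.5, and power Φ(√4.5 − 1.96) ≈ 57%, close to the simulated 60%. The most that any two-way split keeps is 64%, at 50/50.

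**Effect of allowing curvature.** The last column tests one linear term. An overall test with two degrees of freedom (linear and curved terms) has critical value 5.99. With the same noncentrality of about 8.2, its power is about 73%. For diameter at OR 1.4 the same step gives about 73% (median 6 mm) and 76% (median 7 mm). The gain over Fisher narrows but remains.

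**The opposite truth.** If risk is 7.1% below 65 and 11.7% from 65, flat within each group, Fisher has 61% power and a linear age term 41%.

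**The case against.** The strongest case against is that the registry is descriptive. It is sized on interval width, states no subgroup power or significance level, and does not name finding predictors of retreatment as an aim. The shell shows every level's rate and interval, so a difference between groups is visible whatever the test. That stands, and it limits this to a missed efficiency. It does not remove the point, because the plan still commits to p-values.

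The power figures also favour the measured-value test by construction, since the data were generated with the gradient that it assumes. That stands too; the step at 65 reverses the ranking by 20 points.

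Availability is only partly shown. Age is listed as a number, but millimetre diameter appears in neither the Lesion Evaluation table nor its listing. The class limits imply that it is measured, not that it is kept. If only classes are held, what can be recovered is the 3 to 6 points from a trend test.

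Two stronger readings are tempting. A reader might infer that the tests ignore order throughout. Age and neck width have two levels and so no order to lose, and the rank tests for kickout use the order of that outcome. Only the size classes are affected. A reader might also infer that neck width should be tested in millimetres instead. The wide class is a composite with the dome-to-neck ratio, so neck millimetres alone would test a different variable.

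**Conclusion.** The point holds as a cheap improvement. For retreatment, age and aneurysm size are tested only after grouping. Under a smooth gradient this gives up roughly 20 to 30 points of power, nearly all of it from grouping. The size of the loss rests on assumed distributions, on assumed odds ratios of 1.25 to 1.5 per SD, and on a monotone effect; allowing curvature recovers somewhat less than the linear figures suggest. If risk steps at the cut, the planned test is the better one.

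The documents do not support calling the planned tests invalid, or the measured-value test better in all circumstances. No stated figure is wrong. Only retreatment was simulated, so nothing here is claimed for occlusion, safety or kickout.

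**What to change.** Leave the prespecified groups, intervals and Fisher p-values in the subgroup tables as they are. Putting a regression p-value in their place would leave a p-value that does not test the groups displayed.

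Add to SAP section 9 a separately labelled supplementary analysis of retreatment:

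- A logistic model on age in years, with a curved term, in all subjects. Report the overall p-value, the odds ratio with its 95% interval and the fitted curve.
- Where millimetre values are recorded, a logistic model on log largest diameter, with a curved term, in subjects with an aneurysm. Fit it separately, so that subjects without an aneurysm are not dropped from the age model.
- Where only the size class is held, a Cochran-Armitage trend test across the three classes.

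Keep the neck-width class as defined, and do not substitute neck millimetres for it.

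The cost is a few lines of SAP text and SAS code. Age needs no new data, and SAP section 13 already provides for recording changes. The downsides are an assumed functional form, which the curved term relaxes at some cost in power, and a few more p-values to report.

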## 10 Safety Analysis

### 10.1 Primary Safety Analysis

The primary safety endpoint is the proportion of subjects who experience at least one procedural (within 24 hours of arterial puncture) device-related serious adverse event.

Frequency counts and percentages of subjects experiencing a procedural device-related serious adverse event will be provided. A 95% two-sided binomial proportion confidence interval will be reported using a normal approximation to the binomial.

### 10.2 Analysis of Adverse Events

Only adverse events that are related to the procedure or device, unanticipated adverse device effects (UADE), and all serious adverse events (SAE) from consent through registry exit are reportable under the SMART protocol. Reported adverse event data will be presented for each subject, including actions taken, causality (if appropriate), outcome, seriousness, severity, and start and end dates. The onset of adverse events will also be shown relative (in number of days) to the day of treatment. All adverse events will be reported based on the assessment from the clinical study sites.

Rates of device or procedure related adverse events and serious adverse events will be calculated, broken down by category. These reports will count only the most severe adverse event for each subject and only those categories with at least 3% subjects included. Tabulations and descriptive statistics will be produced, including an analysis by time period: (1) intraprocedural or within 24 hours of procedure and (2) after 24 hours post-procedure.

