#### 5.5.2.1 Definitions

- **Adverse Event (AE)** : An *AE* is any undesirable clinical event occurring to a patient, during a clinical trial, whether or not it is considered related to the device. This includes a change in a patient's condition or laboratory results which has or could have a deleterious effect on the patient's health or well-being.
- **Adverse Device Effect (ADE)**: An adverse device effect related to registry device(s).
- **Serious Adverse Event (SAE)**: A *SAE* is an event that:
  - a. Led to death
  - b. Led to a serious deterioration in the health of the patient that:
    - Resulted in life-threatening illness or injury
    - Resulted in permanent impairment of a body structure or a body function
    - Required in-patient hospitalization or prolongation of existing hospitalization
    - Resulted in medical or surgical intervention to arrest permanent impairment to body structure or a body function
    - Led to fetal distress, fetal death or a congenital abnormality or birth defect
- **Unanticipated Adverse Device Event (UADE)**: An event that has an Adverse Device Effect, the specificity or severity of which is

not consistent with the risk information described in the *Instruction for Use* or the clinical protocol.

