### 5.5.2.3 Adverse Event Severity

For the purposes of this trial, the investigator will use the following definitions to rate the severity of each adverse event.

- **Mild:** Awareness of a sign or symptom that does not interfere with the patient's usual activity or is transient, resolves without treatment and with no sequelae
- **Moderate:** interferes with routine activity and/or requires symptomatic therapy
- **Severe:** Severe discomfort and significant impact on the subject's ability to perform routine activities despite symptomatic therapy

Minimum requirements of data to be recorded are: type of event, duration of event (start through end), severity, seriousness, action taken, outcome and, if appropriate, causality.

The Investigator is required to report any device or procedure related AE, UADE and/or SAEs to the Sponsor or its designee as soon as possible, but no later than 24 hours after the event is known. All serious adverse events or serious device effects must document an explanation of any medical treatment administered. The form must be completed and submitted to the Sponsor or its designee within five working days.

An event need not be reported as a SAE if it represents only a relapse or an expected change or progression of the condition that was the cause of treatment without any other symptoms and signs than those present before treatment. This type of event is considered an AE, and may not be reportable.

When appropriate, the IRB/EC shall be informed by the investigator about serious adverse events and adverse device effects associated with the use of the product, and Penumbra is responsible for informing the Health Authorities and other investigators of such events as appropriate.

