### Serious Adverse Events

| Subje ct  | SO C / PT / Name of Event | Date of Onset | Time Period  | Outco me   | Date Resolved or Other, Specify | Sever ity            | Relationship to Disease State/Angio graphic Procedure                       | Relatio nship to SMART / PC 400 / POD Coil System  | Action Taken  | Other, Spec ify | Classific ation of Event  | Did event cause the subje ct to withd raw from regist ry? |
|-----------|---------------------------|---------------|--|--|---------------------------------|----------------------|---|--|---|-----------------|---|---|
| 99999-999 | X                         | DDMON YYYY    | Intraprocedural or within 24 hours of Procedure
After 24 Hours Post Procedure | Resolved Unresolved (Event Continuing)
Death due to this event
Unresolved (Death Due to Other Event)
Unresolved (at time of registry exit/study closure)
Other | DDMON YYYY or <Specify text>    | Mild Moderate Severe | Unrelated Possible Probable Definite / Unrelated Possible Probable Definite | Unrelate d Possible Probabl e Definite / Unrelate d Possible Probabl e Definite / Unrelate d Possible Probabl e Definite | None Remedial Therapy Medical Procedure Hospitalization Other | <Specify text>  | Death Permanent impairment or damage Requires hospitalization or prolongation of existing hospitalization Life threatening Medical or surgical impairment to prevent permanent impairment or damage | Yes No  |

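### SAP 10.2 applies a 3% category cut-off and a most-severe-event-only count to the by-category safety summaries without exempting serious events, so SAE types seen in up to 29 of 1,000 subjects drop out of the summary

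*SAP*

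**What the plan says.** SAP 10.2 (Analysis of Adverse Events) names two sets of rates to be given by category: device- or procedure-related adverse events, and SAEs. The next sentence limits both: "These reports will count only the most severe adverse event for each subject and only those categories with at least 3% subjects included". No exception is made for serious events. The text does not say whether a category is a SOC or a PT, or whether the 3% is judged within one table or on a pooled rate. A further sentence introduces tabulations, "including an analysis by time period: (1) intraprocedural or within 24 hours of procedure and (2) after 24 hours post-procedure", without saying whether the cut-off carries over to them.

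Other places that bear on the point:

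- SAP 2 (Sample Size): "A 1.7% rate of procedural device-related serious adverse events is assumed based on data on file at the sponsor". The stated 95% CI is 0.93% to 2.5% at about 1,000 subjects.
- SAP 10.1: the primary safety endpoint is the proportion of subjects with at least one "procedural (within 24 hours of arterial puncture) device-related serious adverse event".
- Protocol 5.5.2.3 lists severity and seriousness as separate items to record: "duration of event (start through end), severity, seriousness, action taken, outcome". Protocol 5.5.2.1 defines seriousness by consequence, for example "Required in-patient hospitalization or prolongation of existing hospitalization". The SAP appendix listing of SAEs accordingly allows each severity grade: "Mild Moderate Severe".
- Protocol 9.3 plans incidence by category and seriousness and mentions no cut-off.
- The SAP appendix shells for SAEs and for the two time periods have SOC and PT rows and show no cut-off. The two time-period shells say serious in the title but not in the rows, and the matching listings omit the word.

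**The concern.** A frequency cut-off is a way to shorten tables of common, mostly minor events. Here it also covers serious events, and it is set above the total rate that the SAP itself assumes for its key serious event. A reader of the summary tables could see an overall SAE percentage with few or none of the event types behind it.

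The counting rule adds a second loss. As written, each subject contributes one event, so a subject with two different SAEs disappears from one of the two categories. Severity is graded separately from seriousness. In a report that mixed serious and non-serious related events, a severe non-serious event could therefore displace a moderate SAE.

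Because 10.2 leaves the scope and level of the cut-off open, two programmers could also produce different safety tables from the same data.

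**Working it through.** **Inputs.** n = 1,000 (Protocol 9.1, SAP 2); cut-off 3% (SAP 10.2); assumed rate of procedural device-related SAEs 1.7%, with stated limits 0.93% to 2.5% (SAP 2); normal-approximation intervals (SAP 2).

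**1. The plan's own interval.** Formula: p ± 1.96 × √(p(1 − p)/n).

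- Retreatment, p = 0.083: half-width 0.0171, giving 6.59% to 10.01%. This matches the stated 6.6% to 10.0%.
- Safety, p = 0.017: half-width 0.0080, giving 0.90% to 2.50%. The upper limit matches; the lower is 0.03 points below the stated 0.93%. Both stated limits reproduce if the unrounded rate was between 1.734% and 1.740%, which rounds to 1.7%. The difference does not affect what follows.

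**2. What the cut-off removes from the SAE summary.** 0.03 × 1,000 = 30 subjects are needed, so the largest category left out has 29, or 2.9%. Its 95% CI is 0.029 ± 1.96 × √(0.029 × 0.971/1,000) = 1.9% to 3.9%.

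The documents give no SAE rate by category, so the true rates below are assumptions that show the range. The chance that a category is shown is the exact binomial P(X ≥ 30 | n = 1,000):

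| True category rate | Chance of being shown |
|---|---|
| 1% | 0.00002% |
| 2% | 2.1% |
| 3% | 53% |
| 4% | 96% |

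**3. The device-related block of the 24-hour table.** This step assumes that the cut-off reaches the time-period tables and is judged inside that block. Expected subjects with such an SAE, all categories together: 0.017 × 1,000 = 17, against 30 needed. No category can exceed the total, so the most favourable case puts every event in one category:

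| Subjects | Cut-off | Expected at 1.7% | P(reach cut-off) at 1.7% | P at 2.5% |
|---|---|---|---|---|
| 1,000 | 30 | 17 | 0.25% | 17.9% |
| 900 | 27 | 15.3 | 0.40% | 19.4% |
| 800 | 24 | 13.6 | 0.63% | 21.0% |

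The rows for 900 and 800 are assumed smaller denominators. If a category held half of the affected subjects (also an assumption), the chance at n = 1,000 is below 0.002% at either rate.

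**4. Other ways of judging the 3%.** If device- and procedure-related events are judged together, or a pooled rate is used, a category holding all 17 expected subjects needs 30 − 17 = 13 more from other events. The documents give no procedure-related rate, so the chance of that cannot be computed.

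**5. The most-severe-only rule.** Counting one event per subject can remove a subject from a category but never add one. The direction is downward. The documents do not say how many subjects have SAEs in more than one category, so the size is unknown.

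**The case against.** The strongest objection concerns the 24-hour table. A reader might infer from 17 against 30 that this table will show no event types. The documents do not support that as a general statement. The shell covers device- and procedure-related events, with a combined row and a block for each, whereas the 1.7% describes device-related SAEs only. A category could reach 3% through procedure-related events. The cut-off may also not reach the time-period tables at all: it is attached to the rates by category, the time-period tabulations come in a separate sentence, and the shells show no cut-off. If these tables hold non-serious events too, which the mismatch between titles and rows leaves open, 1.7% describes only part of their content. This objection stands, so the 24-hour result is stated only under its conditions.

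Second, little is lost for good. The primary safety rate and its interval (SAP 10.1), the death analysis (SAP 10.3) and the listings, which give event name, time period, severity and relationship, are untouched. This also stands, and it limits the point to the summary tables. A listing does not, however, replace an incidence table by event type.

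Third, the counting rule may be meant as the usual once-per-category count at maximum severity, and displacement of an SAE by a non-serious event needs a mixed report. The SAE shell is serious-only, and nothing establishes that the others are mixed. Displacement is therefore a possibility, not a finding. The text as written still says one event per subject.

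Fourth, a reader might see a contradiction with Protocol 9.3, or with the instruction in SAP 14 to list all categories. Neither holds. Protocol 9.3 is silent on cut-offs and the SAP elaborates on it, and the SAP 14 sentence is a general format rule. Nor is the denominator wholly undefined: the shells use all subjects, and SAP 14 ties exhibits to the ITT or PP population.

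**Conclusion.** The point holds for the SAE summary. Followed as written, SAP 10.2 omits every SAE type seen in up to 29 of 1,000 subjects and counts a subject with several different SAEs in one category only. Category incidence can only be understated, by an amount the documents do not allow one to estimate.

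The consequence for the 24-hour device-related SAE rows is conditional. It needs the cut-off to apply to the time-period tables and to be judged inside the device-related block. Under those two conditions, and the SAP's assumed 1.7%, no category would be expected to appear: the chance is at most 0.25%, rising to 17.9% at a true rate of 2.5% with every event in one category. Under the other readings some rows could appear.

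No bias in the primary safety endpoint follows from any of this. It should be fixed because the change is small and the summary of serious events by type is a main safety output of a post-market registry.

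**What to change.** In SAP 10.2:

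- State that for all SAEs, including device- or procedure-related SAEs and in both time periods, every SOC and PT with at least one subject is tabulated. Each subject is counted once per SOC and once per PT, with no 3% cut-off and no most-severe-only rule.
- If a 3% cut-off is kept, confine it to non-serious related events, and state the table and the level (SOC or PT) at which it is judged.
- Use maximum severity only in a separate severity table.

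In the SAP appendix, make the titles and rows of the two time-period shells and the two matching listings agree on whether they hold serious events or all related events.

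SAP 14 needs no change. The cost is wording in the SAP and shells and longer adverse event tables; no new data are needed. The change should be made before the SAP is signed off, which SAP 1 places before database lock.
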